## 4.6. Other Analyses

### 4.6.1. Subgroup analyses

The list of subgroups below will be used in descriptive summaries of baseline characteristics and may be examined for study outcomes. Summary statistics (n(%)) for the number of responders of the HBsAg <LLOQ response rate will be reported by subgroups. No statistical comparison between subgroups will be performed.

If the percentage of participants is small within a particular subgroup, then the subgroup categories may be redefined. Given the small sample size of this study, if all subjects fall into one single subgroup category, then subgroup analyses for study outcomes will not be necessary and therefore will not be performed. Additional subgroups of clinical interest may also be considered.

Subgroup	Categories
Baseline HBsAg	Low ( $\leq 3 \log_{10}$ IU/mL), High ( $>3 \log_{10}$ IU/mL) $\leq 3, >3-3.5, >3.5-4$ and $>4$ Low ( $\leq 3000$ IU/mL), High ( $>3000$ IU/mL)
Duration of Hep B Infection	$<5$ years, $\geq 5$ years - $<10$ years, $\geq 10$ years - $<20$ years, $\geq 20$ years
Hep B Infection Route	Vertical transmission (e.g., from mother to child); From childhood; Injectable Drugs; Sexual Contact; Blood transfusion; Work exposure (e.g., needle stick); Unknown; Other/prefer not to say
Baseline viral genotype	B, C, Other, Unknown
Baseline BMI	$<30, \geq 30$

## 4.7. Interim Analyses

Data will be incorporated into regular safety reviews by an IDMC and may be used to supplement the safety data review for the Phase IIb B-Clear study [GSK Document Number 2019N420582\_00, Study 209668].

Details of study interim analyses are provided in a separate Interim Analysis Reporting and Analysis Plans.

## 4.8. Changes to Protocol Defined Analyses

Changes from the originally planned statistical analysis specified in the protocol are detailed in [Table 1](#).

**Table 1 Changes to Protocol Defined Analysis Plan**

Protocol Defined Analysis	SAP Defined Analysis	Rationale for Changes
Section 4.3.1.3, single table presented for:  Time to Event Variable • Time to Maximum ALT (ALT must be greater than 3xULN) during 36 weeks of	Now presenting 4 tables instead of one: 

Summary of Time to First Occurrence of Maximum ALT

	

At the time of writing the protocol, it was expected that only one peak in ALT would be seen. We have since seen on other studies, that more than one peak can occur.

Protocol Defined Analysis	SAP Defined Analysis	Rationale for Changes
treatment + follow up Population summary: Turnbull estimate for median Time to Maximum ALT (>3xULN)	
 
Summary of Time to First Occurrence of Maximum ALT during 12 week treatment period
 
Summary of Time to First Occurrence of Maximum ALT after GSK3228836 treatment
 
Summary of Time to Maximum ALT
 
	
 
The first analysis, is the analysis which was originally intended for the study looking at the first peak.
 
The other analyses reflect our newly updated learning for ALT, since the time of writing the protocol.
 

## 5. SAMPLE SIZE DETERMINATION

Approximately 20 participants will be targeted to assign to treatment.

### Primary Endpoint

It is assumed that the number of participants achieving serum HBsAg level <LLOQ by Week 12 without the use of PEG-interferon or other immunomodulator therapies follows a Binomial distribution, with a weakly informative prior beta(0.5, 0.5) for the true response. The precision for a range of true response rates with 95% credible intervals are shown in [Table 2](#).

**Table 2 95% Credible Interval for Percent of Participants achieving HBsAg <LLOQ by Week 12**

Sample size per arm	Number of Participants with HBsAg <LLOQ	Percent of Participants with HBsAg <LLOQ	95% Credible Interval*
20	8	40%	20% – 61%
	10	50%	29% - 71%
	12	60%	39% - 80%
	14	70%	50% - 87%
	16	80%	61% - 94%

\*95% highest posterior density interval

With 20 participants, if the observed response rate is 60%, 70% and 80%, then the lower bound of the 95% credible interval excludes values below 39%, 50% and 61%, respectively. The posterior probability that the percent of participants achieving HBsAg<LLOQ by Week 12 is greater than 50% will be calculated from the implied Beta posterior, given the actual number of responders observed.

The operating characteristics based on at least 75% posterior confidence that the true percentage of participants achieving serum HBsAg level <LLOQ exceeds 50% (desired for further mechanistic exploration of the therapeutic effects of GSK3228836 via intrahepatic immunophenotyping) are shown in [Table 3](#), for various assumed sample sizes and true response rates. A weakly informative prior beta (0.5, 0.5) is used. With a sample size of 20 participants, if there are at least 12 participants achieving HBsAg <LLOQ (observed percent of 60%) then the posterior probability that the true percent is greater than 50% will be greater than 75%.

**Table 3 Study Operating Characteristics by Sample Size**

Criteria	Sample Size	Min N (%) of Participants with HBsAg <LLOQ required for meeting Criteria	Probability of Meeting Criteria if True Response Rate =						
			30%	40%	50%	60%	65%	70%	75%
Probability (true response rate >50%)>75%	10	7 (70%)	1%	5%	17%	38%	51%	65%	78%
	15	9 (60%)	2%	10%	30%	61%	75%	87%	94%
	18	11 (61%)	1%	6%	24%	56%	73%	86%	94%
	20	12 (60%)	1%	6%	25%	60%	76%	89%	96%
	24	14 (58%)	0%	5%	27%	65%	82%	93%	98%
	30	17 (57%)	0%	5%	29%	71%	87%	96%	99%

\* response rate defined as percent of participants achieving HBsAg<LLOQ by Week 12

Based on these operating characteristics, for a true response rate of 60%, the proposed sample-size of 20 has 60% probability of confirming a true rate of at least 50%, and if the true rate is 70%, there is an 89% chance of confirming a true rate greater than 50%.

### Biomarker Endpoints

Given a sample size of 20, the confidence intervals for the ratio in change from baseline in RNAseq (signature) scores between those achieving versus not achieving HBsAg<LLOQ are shown below, assuming a range of effect sizes and between-participant coefficients of variation (CVb).

Example of one scenario with 60% of the participants achieving HBsAg < LLOQ is given below. With relatively smaller between participant variability and larger effect size, a sample size of 20 is appropriate to achieve an acceptable level of precision in detecting the differential responses in biomarker outcomes corresponding to HBsAg responses. For example, in the scenario where 60% of participants achieve HBsAg <LLOQ, if CVb = 0.4, the 95% CI excludes 1 for geometric mean ratios of 0.6 and below, and for 1.7 and above.

12 Participants (60%) Achieving HBsAg<LLOQ							
CVb	95% CI for Ratio of Geometric Mean of Fold Change from Baseline for Participants achieving vs. not achieving HBsAg<LLOQ						
	0.6	0.8	1	1.2	1.4	1.7	2.0
0.2	[0.50, 0.73]	[0.66, 0.97]	[0.83, 1.21]	[0.99, 1.45]	[1.16, 1.69]	[1.41, 2.06]	[1.65, 2.42]
0.4	[0.41, 0.87]	[0.55, 1.16]	[0.69, 1.45]	[0.83, 1.74]	[0.97, 2.03]	[1.17, 2.46]	[1.38, 2.89]
0.6	[0.35, 1.02]	[0.47, 1.36]	[0.59, 1.70]	[0.71, 2.04]	[0.82, 2.38]	[1.00, 2.89]	[1.18, 3.40]
0.8	[0.31, 1.18]	[0.41, 1.57]	[0.51, 1.96]	[0.61, 2.36]	[0.71, 2.75]	[0.87, 3.34]	[1.02, 3.93]
1	[0.27, 1.33]	[0.36, 1.78]	[0.45, 2.22]	[0.54, 2.67]	[0.63, 3.11]	[0.77, 3.78]	[0.90, 4.44]
1.5	[0.21, 1.70]	[0.28, 2.27]	[0.35, 2.83]	[0.42, 3.40]	[0.49, 3.97]	[0.60, 4.81]	[0.71, 5.66]

There are no plans for sample size re-estimation. In certain cases, including but not limited to higher than anticipated drop-out rate, higher than anticipated rates of efficacy, or large variability in ALT flare patterns, the sample size may be increased to no more than 24.

## 6. SUPPORTING DOCUMENTATION

### 6.1. Appendix 1 Study Population Analyses

Unless otherwise specified, the study population analyses will be based on the Enrolled Analysis Set. A summary of the number of participants in each of the participant level analysis set will be provided.

A listing of subjects excluded from any population will be presented.

In this multicentre global study, enrolment will be presented by country and site.

#### 6.1.1. Participant Disposition

A summary of the number and percentage of patients who were screened including screen failures will be provided, and will be based on the Screened Analysis Set. Reasons for failure will be included.

A summary of the number and percentage of participants who completed the study as well as those who prematurely withdrew from the study will be provided. Reasons for study withdrawal will be summarized.

A summary of study intervention status will be provided. This display will show the number and percentage of participants who completed the scheduled study intervention, or who discontinued study intervention prematurely, as well as primary reasons for discontinuation of study intervention.

Summaries of disposition, adverse events leading to withdrawal and reasons for withdrawal will be presented by Study Period, as defined in the Output and Programming Specification.

Listings of reasons for study withdrawal, screen failure and study treatment discontinuation will be provided.

A listing and summary of number of planned and completed FNA's per patient will be presented.

#### 6.1.2. Demographic and Baseline Characteristics

Study population analyses including analyses of participant's disposition, protocol deviations, demographic and baseline characteristics, prior and concomitant medications, nucleos(t)ide treatment starting after randomization, medical history and exposure and treatment compliance will be presented.

Demographic characteristics including sex, age, ethnicity, race, height and weight will be summarized with descriptive statistics.

Baseline characteristics including hypertension, NSAID, TDF/TAF containing medications use, ADV containing medications use, diabetes, eGFR, serum creatinine, urine ACR, platelets, ANC, complement C3, complement C4, complement C5a, complement Bb, C Reactive Protein, MCP-1, c-ANCA, p-ANCA and subgroup categories listed in Section 4.6.1 will be summarized with descriptive statistics.

Hepatitis B characteristics, as collected on the Hep B Disease Characteristics eCRF, will be summarized using descriptive statistics, and will be listed.

A table and listing of nucleos(t)ide treatment at baseline will be presented.

### **6.1.3. Protocol Deviations**

Important protocol deviations will be summarized.

Protocol deviations will be tracked by the study team throughout the conduct of the study. These protocol deviations will be reviewed to identify those considered as important as follows:

- Data will be reviewed prior to freezing the database to ensure all important deviations are captured and categorised in the protocol deviations dataset.
- This dataset will be the basis for the summaries of important protocol deviations.

### **6.1.4. Prior and Concomitant Medications**

Concomitant medications will be coded using the GSK Drug dictionary. The summary of concomitant medications will be provided by ingredient, i.e., multi-ingredient medications will be summarized for each individual ingredient rather than a combination of ingredients. The summary will be created using ingredient base names, i.e., ingredients with the same base name but different salt will appear under one base name in the summary. Anatomical Therapeutic Chemical (ATC) classifications will not appear in the summary.

A prior medication is defined as any medications that is ended prior to the date of first dose of study drug.

Medications initiated after the first dose of study drug or initiated prior to the first dose of study drug and continued after the first dose of study drug will be counted as concomitant medications. A medication that cannot be determined as prior or concomitant medication due to partially or completely missing start/stop date will be counted as both prior and concomitant medication.

### **6.1.5. Study Intervention Compliance**

A summary of overall compliance for GSK3228836 based on the exposure data will be produced. Overall compliance will be summarized using descriptive statistics as well as the categories <80% and  $\geq 80\% - 100\%$ .

Compliance will be summarized both in terms of number of injections administered and total dose received during the planned on-treatment period.

Study intervention Compliance (%) = [Number of actual doses / Number of planned doses] \*100.

Study dose Compliance (%) = [Actual Total Dose / Planned Total Dose] \* 100

#### **6.1.6. Additional Analyses Due to the COVID-19 Pandemic**

A participant is defined as having a suspected, probable or confirmed COVID-19 infection during the study if the answer is “Confirmed”, “Probable” or “Suspected” to the case diagnosis question from the COVID-19 coronavirus infection assessment eCRF. Numbers of participants with a suspected, probable or confirmed COVID-19 infection, and of COVID-19 test results will be summarized.

Additionally, if greater than 5% participants have a suspected, probable or confirmed COVID-19 infection, the following data displays will be produced:

- Summary of current (and/or past) medical conditions for participants with COVID-19 adverse events.
- Summary of baseline characteristics for participants with COVID-19 adverse events.

## 6.2. Appendix 2 Data Derivations Rule

### 6.2.1. Criteria for Potential Clinical Importance

Grading categories for laboratory tests are determined using the DAIDS grading system Version 2.1 [National Institute of Allergy and Infectious Diseases. Division of AIDS, 2017].

No Laboratory tests values of potential clinical importance are defined. Laboratory values outside of normal range will be summarized and listed.

### 6.2.2. Study Period

Assessments and events will be classified according to the time of occurrence relative to the study intervention period. Off Treatment Day 1 occurs 7 days after the last study treatment dose received, regardless of whether the participant completes treatment as planned or the participant is withdrawn from study treatment.

Study Intervention Period	Definition
Pre-Treatment	Date  ≤ Study Treatment Start Date
On-Treatment	Study Treatment Start Date < Date  ≤ Off Treatment Day 1 – 1 day
Post-Treatment	Date  ≥ Off Treatment Day 1

1 Date is the start date of the assessment/event.

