### 4.5.2. Adverse Events

An adverse event (AE) is considered treatment emergent if the AE onset date is on or after treatment start date. If AE start date is completely missing and the end date is on or after

the treatment start date, the AE will be assumed to be treatment emergent. All AE summaries will be based on treatment emergent events unless otherwise specified.

Adverse events will be coded using the latest version of MedDRA coding dictionary, to give a preferred term and a system organ class. These preferred terms and system organ classes will be used when summarising the data. The severity of AEs and SAEs will be determined by the investigator according to the DAIDS grading system Version 2.1 [[National Institute of Allergy and Infectious Diseases. Division of AIDS, 2017](#)], unless specified otherwise in the protocol.

For AEs by maximum grade summary tables, if a participant reports an AE more than once within an SOC/PT, the AE with the most severe intensity will be included in summaries. Relationship to study treatment, as indicated by the investigator, is classified as “not related” or “related”. Adverse events with a missing relationship to study treatment will be regarded as “related” to study treatment.

The following AE summaries will be presented:

1. AEs overview: summarize the number and percentage of participants with any adverse event, AEs related to study treatment, AEs leading to permanent discontinuation of study treatment, withdrawal from the study, any serious adverse events (SAE), SAEs related to study treatment, fatal SAEs and fatal SAEs related to study treatment.
2. All AEs by system organ class (SOC) and preferred term (PT)
3. All AEs by SOC and PT and maximum grade
4. All drug-related AEs by SOC and PT
5. All drug-related AEs by SOC and PT and maximum grade
6. Serious AEs (SAEs) by SOC and PT
7. AEs leading to withdrawal from the study by SOC and PT
8. AEs leading to permanent discontinuation of investigational product by SOC and PT
9. AEs leading to withdrawal from the study by SOC and PT and maximum grade
10. AEs leading to permanent discontinuation of investigational product by SOC and PT and maximum grade
11. Fatal AEs by SOC and PT
12. AEs by overall frequency
13. Non-serious AEs by SOC and PT
14. Non-serious drug-related AEs by overall frequency
15. Serious fatal and non-fatal AEs by overall frequency

Number of participants with AEs will be summarized if it is not specified otherwise.

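### The SAP's Study Period rule labels an adverse event starting on the day of first dose Pre-Treatment, while its adverse event rule calls the same event treatment emergent

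*SAP*

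**What the plan says.** SAP 6.2.2 opens with its scope: "Assessments and events will be classified according to the time of occurrence relative to the study intervention period". Its table places a record in Pre-Treatment when its date is "≤ Study Treatment Start Date" and opens On-Treatment with "Study Treatment Start Date < Date", so the day of first dose belongs to Pre-Treatment. A footnote fixes the variable being compared: "Date is the start date of the assessment/event". There is no clock-time tie-break and no exception for events.

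SAP 4.5.2 draws the line on the other side of the same day: "An adverse event (AE) is considered treatment emergent if the AE onset date is on or after treatment start date". It adds: "All AE summaries will be based on treatment emergent events unless otherwise specified".

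Three other places bear on the point:

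- SAP 6.1.1 says that "adverse events leading to withdrawal and reasons for withdrawal will be presented by Study Period". The sentence then refers the definition of Study Period to the Output and Programming Specification, not to 6.2.2.
- SAP 6.2.7 allows partial dates to be imputed in order to place data in study phases. It sets many partial AE start dates to the treatment start date.
- SAP 4.1.2 treats Day 1 assessments with no recorded time as taken before the first dose. It says nothing comparable about events.

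**The concern.** A Day 1 laboratory sample is normally drawn before the injection, so counting it as Pre-Treatment is sensible. An AE is different. The Schedule of Activities has injection site reactions assessed on Day 1, and Protocol 8.2.9.5 requires any that are found to be reported as AEs. The same section describes them as the most commonly reported treatment-related AE in earlier studies of the drug. Under Protocol 8.2.6.1, an event before the first administration is recorded as an AE only if it is judged related to study participation. An AE dated Day 1 is therefore more likely to follow the injection than to precede it.

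Under 6.2.2 such a reaction would sit in the same period as events from pre-treatment procedures, such as the baseline fine needle aspiration. At stake is the consistency of period labels for first-dose events in a study of about 20 participants that has safety as a stated objective.

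**Working it through.** No sample size or power figure is involved, so the check is a comparison of the two rules over all plausible onset dates.

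**Inputs**

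- S = treatment start date, which is Study Day 1 (SAP 6.2.3).
- L = date of last dose. The planned last dose is on Day 78 (Schedule of Activities).
- Off Treatment Day 1 = L + 7 days (SAP 6.2.2). With L on Day 78 this is 78 + 7 = Day 85, so On-Treatment ends on Day 84.

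**Rules, with d the onset date**

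- SAP 6.2.2: Pre-Treatment if d ≤ S; On-Treatment if S < d ≤ L + 6; Post-Treatment if d ≥ L + 7.
- SAP 4.5.2: treatment emergent if d ≥ S.
- The rules conflict when an AE is treatment emergent and Pre-Treatment, or not treatment emergent and in a later period.

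**Result with last dose on Day 78**

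| Onset | 6.2.2 period | Treatment emergent (4.5.2) | Agree? |
|---|---|---|---|
| Study Day -1 | Pre-Treatment | No | Yes |
| Study Day 1 | Pre-Treatment | Yes | **No** |
| Study Day 2 | On-Treatment | Yes | Yes |
| Study Day 84 | On-Treatment | Yes | Yes |
| Study Day 85 | Post-Treatment | Yes | Yes |

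From 45 days before S to 259 days after it there are 45 + 1 + 259 = 305 onset dates. Exactly one conflicts: S itself. The periods otherwise meet without gap or overlap. For a participant who receives only the Day 1 dose, Off Treatment Day 1 is 1 + 7 = Day 8, and Study Day 1 again conflicts.

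**With the event boundary moved**

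Take Pre-Treatment as d < S and On-Treatment as S ≤ d ≤ L + 6. None of the 305 dates conflicts.

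**Partial dates**

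Under SAP 6.2.7, an AE with a missing start day in the month of first dose is given start date S, unless a complete stop date precedes S. A missing day and month is handled the same way by year. Setting d = S makes the AE treatment emergent. If that imputed date is also used for study phase, 6.2.2 makes the AE Pre-Treatment, even if it truly began later.

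**The case against.** The strongest reply is that the mismatch may never reach a table.

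- **Main AE summaries.** All 15 listed in SAP 4.5.2 follow the treatment-emergent flag, which includes Day 1. The event-characteristics summaries for AEs of special interest use the post-baseline period. This stands. A reader might infer that first-dose reactions drop out of the safety tables, but the documents do not support that.
- **By-period summaries.** A reader might infer that every by-period output carries the error. SAP 6.1.1 takes its Study Period from the Output and Programming Specification, which may define it differently. The AE-withdrawal display would be affected only if the specification copied 6.2.2 and a Day 1 AE led to withdrawal. Protocol Table 5 describes earlier injection site reactions as Grade 1 and 2, so an ordinary first-dose reaction would not usually get there. This stands as a limit on reach.
- **Analyses that cite 6.2.2.** The time-to-maximum-ALT analyses in SAP 4.3.1.3 do so, but ALT is an assessment. The present boundary is reasonable there and agrees with the baseline rule in SAP 4.1.2. This also stands.
- **Partial dates.** SAP 6.2.7 permits imputation for phase assignment and does not require it, so that extension is conditional.

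None of this removes the contradiction. Section 6.2.2 is the only Study Period definition in the SAP, it names events, and it gives them no exception.

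**Conclusion.** The SAP is wrong as written on a narrow point. For an AE with onset on the treatment start date, 6.2.2 and 4.5.2 give incompatible labels. The conflict covers one calendar date per participant, plus any AE imputed to that date and then assigned to a phase with it.

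The practical effect is confined to displays or derivations that apply the 6.2.2 period to events. The main AE summaries are sound. Whether the disposition and AE-withdrawal summaries are affected cannot be settled without the Output and Programming Specification.

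No percentage should be attached. Day 1 is 1 of 14 planned dosing days (1/14 = 7%), and a reader might take that as the share of AEs misclassified. It is a share of dosing days, not of events. A Day 1 AE that truly precedes the injection is correctly labelled Pre-Treatment, and a reaction to the first dose that starts the next day is On-Treatment. The documents also give no basis for saying that acute reactions first appear at this dose.

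The conclusion assumes that 6.2.2 means what its table and footnote say: calendar dates, for events as well as assessments.

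**What to change.** Split the rule in SAP 6.2.2 by type of record.

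- **AEs:** Pre-Treatment when the onset date is before the treatment start date; On-Treatment from the treatment start date through the day before Off Treatment Day 1; Post-Treatment unchanged. Where onset time is collected, use it to keep truly pre-dose Day 1 events in Pre-Treatment.
- **Assessments:** keep the present boundary for those assumed to be pre-dose, consistent with SAP 4.1.2.
- **Output and Programming Specification:** align its Study Period definition, and state whether AE start dates imputed under SAP 6.2.7 are used to assign study phase.

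If onset time is used in 6.2.2, put the same tie-break in 4.5.2; otherwise the two rules will differ again for pre-dose Day 1 events. Concomitant medications need no change, because SAP 6.1.4 has its own rule for them.

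The cost is about one row of SAP wording, a matching entry in the specification, and negligible programming. No data collection changes.
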